#### **14.1 Adverse Events**

All adverse events will be collected, whether potentially related or unrelated to study drug use. Study drug includes the investigational drug under evaluation and placebo given during any stage of the study.

Treatment-emergent adverse events (TEAE) are defined as any event that occurs on or after the day that randomized study treatment is initiated. Adverse events recorded in the CRF which began prior to treatment will not be included in the summary tables but will be included in the AE data listings.

The severity of each AE will be evaluated as Mild, Moderate or Severe.

The relationship of each AE to the study drug will be determined by the Investigator as None, Possibly Related, or Probably Related.

Action taken with study drug will be classified as None, Permanently Discontinued, Temporarily Discontinued, or Other.

An overall summary will be presented that includes the number of events and the number and percentage of subjects who experienced at least one TEAE, by treatment group. This summary will also include breakdowns of TEAEs further categorized as ocular or non-ocular, treatment-related TEAEs, serious AEs (SAE), and TEAEs leading to early treatment discontinuation.

Additional summaries of TEAEs will be provided showing the number and percentage of subjects who experienced at least one TEAE by treatment group and over all subjects. Non-ocular TEAEs will be summarized using discrete summary statistics and presented by treatment group at the subject and event level by SOC and PT. Ocular TEAEs will be similarly summarized at the subject level. If a subject reports the same PT multiple times within the same SOC, that PT will only be reported once within that SOC. As with the PT, if a subject reports multiple conditions within the same SOC, that SOC will only be reported once. In the summary, SOCs will be listed in ascending alphabetical order; PTs will be listed in order of descending frequency for all subjects within each SOC.

Separate summaries will be provided for the following categories of AEs:

- Overall AE Summary
- TEAEs
- TEAEs by Relationship to Study Medication
- Treatment Emergent SAEs

All AEs will be presented in a subject listing.

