## III. SUBJECT SELECTION

The plan is to screen 42 patients in order to achieve a study completion of 33 patients, 2:1 active drug:placebo. Subjects at least 18 years of age with a diagnosis of chronic ocular GvHD and fulfilling certain inclusion and exclusion criteria will be eligible. We anticipate that [name], Principal Investigator, Ophthalmologist at MEE Longwood will have a sufficient number of eligible patients to enable enrollment from one site.

The inclusion and exclusion criteria are as follows:

Inclusion Criteria:	

1. Male or female of any race, at least 18 years of age at Visit 1 Screening.

2. Has the diagnosis of chronic ocular GvHD.

3. Has the NIH Consensus Eye Score of at least 2.

4. On the GLIA Ocular Surface Disease Symptoms Questionnaire at Screening, has ocular discomfort at a severity score of moderate or more, and at least one other symptom at a severity of moderate or more.

5. One or more signs from the list of chronic ocular GvHD signs below.

6. Has provided verbal and written informed consent.

----------------------------	--

	

7. Be able and willing to follow oral and written instructions, including participation in all study assessments and visits.

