## **8.3 Definition of Baseline**

For the Study Treatment Phase, baseline is defined as the last measurement prior to the first dose of study medication.

For the Cross-over Phase, baseline is defined as the last measurement prior to the first dose of Pro-ocular™ 1% topical gel, which is expected to start on the day after Visit 5.

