## 19. Tables, Listings and Figures

Tables	Title	Population
Table 14.1.1	Subject Disposition	All Enrolled Subjects
Table 14.1.2	Demographic and Iris Color	ITT Population

Table 14.1.3.1	Ocular Medical History	ITT Population
Table 14.1.3.2	Non-Ocular Medical History	ITT Population
Table 14.1.4.1	Ocular Concomitant Medications Intent-to-Treat Population	ITT Population
Table 14.1.4.2	Non-Ocular Concomitant Medications Intent-to-Treat Population	ITT Population
Table 14.1.5	Study Drug Exposure in Days	Safety Population
Table 14.2.1.1	GLIA Ocular Surface Disease Symptoms Questionnaire, in Clinic by Eye	ITT Population
Table 14.2.1.2	GLIA Ocular Surface Disease Symptoms Questionnaire, in Clinic with Combined Eyes	ITT Population
Table 14.2.2.1	GLIA Ocular Surface Disease Symptoms Questionnaire, Daily Diary by Eye	ITT Population
Table 14.2.2.2	GLIA Ocular Surface Disease Symptoms Questionnaire, Daily Diary with Combined Eyes	ITT Population
Table 14.2.3.2	Modified SANDE - Symptom Assessment iN Dry Eye (SANDE) Questionnaire by Eye	ITT Population
Table 14.2.3.3	Modified SANDE - Symptom Assessment iN Dry Eye (SANDE) Questionnaire with Combined Eyes	ITT Population
Table 14.2.4.1.1	Slit Lamp Biomicroscopy Without Staining by Eye	ITT Population
Table 14.2.4.1.2	Slit Lamp Biomicroscopy Without Staining with Combined Eye	ITT Population
Table 14.2.4.1.3	Slit Lamp Biomicroscopy Without Staining – Shift Table	ITT Population
Table 14.2.4.2.1	Corneal and Conjunctival Fluorescein Staining Examination by Eye	ITT Population
Table 14.2.4.2.2	Corneal and Conjunctival Fluorescein Staining Examination with Combined Eye	ITT Population
Table 14.2.5	National Institute of Health (NIH) Eye Score	ITT Population
Table 14.2.6	Daily Use of Eye Drops	ITT Population
Table 14.2.7	TearScan Examination	ITT Population
Table 14.2.8	Visual Acuity in LogMAR Units	ITT Population
Table 14.2.9	Facial Presentation and Blinks per Minute	ITT Population
Table 14.3.1.1	Overall Summary of All Treatment-Emergent Adverse Events (TEAEs)	Safety Population
Table 14.3.1.2	Treatment-Emergent Adverse Events (TEAE) by System Organ Class (SOC) and Preferred Term (PT)	Safety Population
Table 14.3.1.3	Treatment-Emergent Adverse Events (TEAEs) by System Organ Class, Preferred Term, and Relationship to Study Drug	Safety Population
Table 14.3.1.4	Serious Treatment-Emergent Adverse Events (TEAEs) (Including Death) by System Organ Class (SOC) and Preferred Term (PT)	Safety Population

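### The TEAE rule in SAP 14.1 has no worsening clause, so on-treatment worsening of a pre-existing condition reaches the adverse-event tables only if staff happen to log it as a new event

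*SAP*

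**What the plan says.** SAP 14.1 classes an adverse event as treatment-emergent if it is "any event that occurs on or after the day that randomized study treatment is initiated". It then states that "Adverse events recorded in the CRF which began prior to treatment will not be included in the summary tables". Such events appear only in the subject listings. Neither sentence mentions a change in severity.

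SAP 19 plans four adverse-event tables, 14.3.1.1 to 14.3.1.4: overall, by system organ class and preferred term, by relationship, and serious events. All four are restricted to TEAEs.

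Protocol III requires an NIH eye score of at least 2 and at least one ocular GvHD sign. It also requires that the subject "has ocular discomfort at a severity score of moderate or more, and at least one other symptom at a severity of moderate or more".

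SAP 14 analyses safety separately for the Study Treatment Phase and the Placebo Cross-over Phase. SAP 8.3 resets the reference for the second: "For the Cross-over Phase, baseline is defined as the last measurement prior to the first dose of" Pro-ocular. The TEAE definition has no matching reset; its only anchor is the start of randomized treatment.

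**The concern.** A TEAE definition normally has two limbs: events that start after the first dose, and conditions already present that get worse after it. Only the first is here, and the exclusion sentence works against the second. This matters more than usual in this trial, because everyone enrolled already has symptomatic eye disease. An ocular harm could well appear as an existing problem getting worse rather than as a new diagnosis.

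Safety is half of the primary objective (SAP 2), and the TEAE tables are where event incidence is compared between arms. An event that began before treatment and turned severe or serious on it would appear in a listing but in no between-arm count. In the Cross-over Phase, an event carried over from placebo that worsens on the active gel has no stated place.

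**Working it through.** The plan gives no figure to reproduce. The check is of the text, followed by one line of arithmetic for scale.

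**1. Can worsening meet the definition?** An event row with a pre-treatment onset date cannot, because the exclusion sentence removes it whatever its later severity. A worsening entered as a separate row with an on-treatment onset date can, because it then occurs after treatment starts. The outcome depends on how it is recorded.

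**2. Do the documents fix how it is recorded?** No.
- Protocol IX.d says that all adverse events are collected, but not how a change in an existing condition is entered.
- The adverse event log in the protocol appendix has one onset date and one severity code per row, with no field or instruction for worsening.
- The Safety Management Plan cited in Protocol IX is not among the documents, so a rule there can be neither confirmed nor excluded.

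**3. How many rows would the exclusion sentence remove?** This cannot be derived, but probably few. The adverse event query is first scheduled post-dose at Visit 2 (protocol schedule; SAP Table 2). Conditions present at entry would mostly sit in medical history (SAP 11.1). For those conditions the gap is different: no stated route takes a worsening from medical history into the adverse event log.

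**4. Where else would worsening show between arms?**

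| Domain | Other planned output | Coverage |
|---|---|---|
| Ocular symptoms | VAS models, clinic and diary (SAP 13.1) | Group means; individual deterioration can be hidden |
| Slit lamp | Models and shift tables (SAP 13.5.3); Safety-population shift table 14.3.5.3 | Good |
| Staining | t-tests and shift tables (SAP 13.5.4) | Good |
| Visual acuity | Change of at least 0.20 logMAR (SAP 14.2) | Visits 1 and 5 only |
| Fundoscopy | Shift tables (SAP 14.4) | Visits 1 and 5 only |
| Systemic GvHD | None beyond laboratory panels | The physician assessment is a safety variable in SAP 2.3, but has no section in SAP 14 and no table or listing in SAP 19 |
| Adverse event severity | None | SAP 2.3 names severity, but no adverse-event table is by severity |

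The eye is partly covered. Clinical worsening of systemic GvHD is not, so the adverse-event tables are the main route for comparing it.

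**5. Cross-over.** An event that began on placebo already counts as a TEAE from the randomized phase. The SAP does not say whether its worsening on open-label Pro-ocular is counted again, moved to the cross-over table or left where it is.

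**6. Scale.** Inputs are 22 Pro-ocular and 11 placebo subjects (SAP 5), assuming that all receive at least one application and so enter the Safety population. One missed subject with no other TEAE lowers that arm's incidence by 1/n:
- Pro-ocular: 1/22 = 0.045, or 4.5 percentage points.
- Placebo: 1/11 = 0.091, or 9.1 percentage points.
- Cross-over group, if all 11 enter: 1/11, or 9.1 percentage points.

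A subject who has another TEAE changes the overall incidence by nothing, though a preferred-term row may still be short by one.

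**The case against.** The strongest reply is that baseline disease is not the same thing as a recorded adverse event. The exclusion applies to rows in the adverse event record, and few are likely to carry a pre-treatment onset. The definition says that an event occurs, not that it begins, so a worsening logged as new satisfies it and nothing forbids such logging. Ocular deterioration is measured repeatedly and compared by arm elsewhere, and excluded events are still listed. Adverse events are summarized descriptively in a 33-subject Phase 2 trial, and the Cross-over Phase is secondary.

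Most of this stands, and it limits the point. Three stronger readings that a reader might draw are not supported:

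- *That all 33 subjects lose events.* Eligibility shows that all have eye disease at entry, not that any has an excluded event. It does not establish systemic GvHD in every subject either.
- *That the rule flatters the gel.* It applies equally to both arms. If the gel works, worsening would be commoner on placebo and the omission would hide a benefit. The direction is unknown.
- *That an event worsening after cross-over can never count for Pro-ocular.* The SAP does not say so; it has no rule assigning the event.

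The reply does not supply a recording requirement. Whether a worsening is tabulated still turns on whether staff open a new row or amend the old one, and systemic GvHD has no alternative summary.

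**Conclusion.** The point holds as a gap in the safety analysis that should be fixed; it is not a fatal flaw. As written, an adverse event with pre-treatment onset that becomes worse on treatment gets no between-arm count, and worsening of a condition held in medical history is counted only through a recording habit that the documents do not set. The exposure is greatest for systemic GvHD and smaller for the eye. Assignment of events that span the cross-over is unspecified.

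The size is 4.5 or 9.1 percentage points for each missed subject with no other TEAE. The total and the direction of any between-arm bias cannot be derived. The conclusion assumes that no recording rule for worsening exists in the Safety Management Plan or other material not supplied. If one does, the recording gap closes, but the exclusion sentence and the cross-over anchor would still need amending.

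**What to change.** Amend SAP 14.1 and the logging instruction:

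1. *A TEAE is an event that begins, or a pre-existing condition or event that worsens in severity, on or after the first application of study drug.*
2. *For the Cross-over Phase the reference is the first open-label application of Pro-ocular. An event that began earlier and worsens after that application is counted in the cross-over table.*
3. Limit the exclusion sentence to events that began before treatment and did not worsen.
4. Log each worsening as a new adverse event row with its own onset date and severity, whether the earlier condition sits in the adverse event log or in medical history.

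The cost is a few sentences, a phase-specific flag in programming, and some review of the adverse event log with queries before database lock. A flag alone cannot recover worsening, because the log holds one onset date and one severity per row. SAP 16 already reports a single early discontinuation, so the trial was under way when the SAP was written. Some worsening dates may not be recoverable for subjects who have completed, and the study report should say so.

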### d. Adverse event reporting guidelines

All adverse events will be collected, whether potentially related or unrelated to study drug use. The adverse events will be categorized according to the latest version of MedDRA (Medical Dictionary for Regulatory Activities) using Common Terminology Criteria (CTCAE). The Safety Management Plan provides guidance for what is considered a serious adverse event, the forms to be completed in such cases, and when a serious adverse event needs to be reported to the FDA.

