**ADVERSE EVENT LOG**

Visit Number	Report date (mm/dd/yyyy)	Adverse event	Relationship to study drug(1, 2, or 3)	Adverse event onset date (mm/dd/yyyy)	Adverse event end date (mm/dd/yyyy)	Severity (1, 2, or 3)	Action taken with study drug(1-, 2, 3, or 4)	Specify, if action taken with study drug="4. Other"	Outcome (1, 2, or 3)	Serious adverse event (Yes/No)

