**Enter numerical responses for following Questionnaire categories**

Relationship to study drug:	Severity:	Action taken with study drug:	Outcome:
1. None	1. Mild	1. None	1. Resolved
2. Possibly related	2. Moderate	2. Permanently Discontinued*	2. Ongoing
3. Probably related	3. Severe	3. Temporarily Discontinued 4. Other(specify)	3. Lost to follow-up

\* Complete study discontinuation form

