### 2.3 Safety Variables

The safety variables include the following:

- Incidence and severity of Adverse events (AE)
- Visual acuity
- Slit lamp biomicroscopy
- Undilated fundoscopy examination
- Intraocular pressure (IOP)
- Systemic assessment by bone marrow transplant (BMT) physician at Dana- Farber Cancer Institute (DFCI)

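### Adverse event severity is a named safety variable with no planned summary by arm, and the adverse event log's outcome codes have no entry for a death

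*SAP*

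**What the plan says.** SAP 2.3 opens its list of safety variables with "Incidence and severity of Adverse events (AE"). SAP 14.1 gives the scale: "The severity of each AE will be evaluated as Mild, Moderate or Severe". It then lists four separate summaries: an overall summary, all treatment-emergent events, those events by relationship to study medication, and treatment-emergent serious events. SAP section 19 matches these with Tables 14.3.1.1 to 14.3.1.4, the last titled "Serious Treatment-Emergent Adverse Events (TEAEs) (Including Death) by System Organ Class (SOC) and Preferred Term (PT").

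The protocol's Adverse Event Log has closed fields for severity, "Severity (1, 2, or 3"), and for outcome, "Outcome (1, 2, or 3"). The key beneath it decodes severity as mild, moderate or severe. It decodes outcome as resolved, ongoing and "3. Lost to follow-up". A further column marks each event as serious or not.

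Protocol IX.d sets a classification standard: "The adverse events will be categorized according to the latest version of MedDRA (Medical Dictionary for Regulatory Activities) using Common Terminology Criteria (CTCAE"). The same paragraph leaves the definition of a serious event, and the forms to complete for one, to a Safety Management Plan that is not among the documents supplied.

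**The concern.** Three things do not fit together.

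- A variable that the SAP names and the log collects has no planned output by treatment group.
- A table that promises to include deaths has no matching outcome code on the form that records adverse events.
- The protocol cites one classification standard, while its own log and the SAP use a severity scale that is not tied to it.

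Safety is half of the stated objective, and the subjects are allogeneic transplant recipients, in whom serious systemic events are foreseeable. If the plan is followed as written, the report will show how many subjects in each arm had an event. It will not show whether the non-serious events in one arm were mostly mild and in the other mostly severe. If a subject dies, the log offers no correct outcome entry, and the SAP does not say which field identifies the death.

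**Working it through.** No figure is stated and none needs to be recomputed. The check sets the passages side by side.

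**1. Severity: named, collected, not tabulated**

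| Item | Collected | Summary by arm |
|---|---|---|
| Relationship to study drug | Log, three codes; SAP 14.1 | Yes: 14.1 list and Table 14.3.1.3 |
| Seriousness | Log, yes/no | Yes: overall summary and Table 14.3.1.4 |
| Severity | Log, three codes; SAP 14.1 | None |

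Of the four summaries listed in SAP 14.1, none is by severity. Of the four adverse event tables in section 19, none is by severity. The breakdowns within the overall summary are ocular or non-ocular, treatment-related, serious, and leading to early discontinuation of treatment; severity is not among them. What remains is the subject listing of all adverse events (Listing 16.2.6). SAP section 16, which records departures from the protocol, does not present this as a decision. Relationship is recorded in the same way and has its own table, so the gap looks like an omission.

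**2. Outcome: no entry for a death**

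The log allows three outcome codes, and none describes a fatal event. SAP 14.1 defines no outcome categories. Table 14.3.1.4 nevertheless names death in its title. Nothing in the supplied documents identifies the field from which a death would be read. The forms for serious events may hold it, but they were not supplied.

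**3. Severity standard: not linked**

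Protocol IX.d cites CTCAE. The protocol's log and SAP 14.1 both use mild, moderate and severe. The SAP does not mention CTCAE in section 14.1, in its abbreviations or in section 16. The SAP states that it was written for protocol version 4.0, whereas the protocol supplied is version 5.1. That difference does not explain the mismatch, because version 5.1 contains both the CTCAE clause and the three-level log. The SAP's statement that it supersedes the protocol concerns statistical analysis methods, not how an investigator rates an event.

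**4. What a severity table could show**

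With 22 and 11 subjects, one subject moves a percentage by 1/22 = 4.5 points in the active arm and 1/11 = 9.1 points in the placebo arm. Such a table describes the data; it does not support inference.

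**The case against.** A reader might infer that life-threatening and fatal events cannot be coded or compared at all. The documents do not support that. Each event carries a yes/no serious flag. Protocol IX.d refers to separate forms for serious events. SAP 14.1 breaks out serious events by treatment group in the overall summary and plans a separate summary of them. Table 14.3.1.4 covers serious events with deaths included, and every event is listed by subject. Nor can it be shown that this table could not be filled, because the forms that may record death are unseen.

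A reader might also infer that specific CTCAE grades are being merged. No passage prints a CTCAE grade range, and the clause in Protocol IX.d speaks of categorizing events without mentioning severity. The documents show only that CTCAE is cited and never tied to the scale in use. The log and SAP do agree with each other on that scale.

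Nor does treatment out to 27 months enlarge the between-arm loss. The randomized comparison lasts 70 days, placebo subjects then receive active drug, and the SAP's analyses end at Visit 7. SAP section 16 reports one early discontinuation, so the effect on the masked-phase tables may be small.

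All of this limits the point without removing it. A serious flag says nothing about the severity of non-serious events, a listing is not a comparison between arms, and the log's outcome codes still have no valid entry for a death.

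**Conclusion.** The concern holds in a limited form. A safety variable named in SAP 2.3 is never summarized by arm: zero of four planned summaries and zero of four tables show it. The log's three outcome codes contain no valid entry for a death, and the SAP does not state where the deaths in Table 14.3.1.4 come from. The CTCAE reference is not reconciled with the scale in use.

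What is lost is the severity distribution by arm and a correct outcome code, not the capture or comparison of serious events as such. The change should be made because the gap concerns a stated safety variable and costs little to close. It does not threaten the efficacy analysis or the serious event summaries.

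This rests on two assumptions: that the printed log is the form in use, and that the Safety Management Plan, which was not supplied, does not already define the severity standard and the source for deaths. If it does, the second and third parts reduce to adding a cross-reference. The missing table stands either way.

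**What to change.** 1. Add to SAP 14.1 and section 19 a table of treatment-emergent events by maximum severity and treatment group, for all events and for treatment-related events, in the Safety population. Count each subject once, at the highest recorded severity. The data already exist, so no event needs to be re-rated. This matters because the investigator unmasks each subject after Visit 5 (SAP 4.2) and could not re-rate those subjects' events masked.
2. Add a fatal outcome code to the Adverse Event Log. State in the SAP whether the deaths in Table 14.3.1.4 are taken from the log or from the serious event form.
3. Reconcile Protocol IX.d, the log's code key and SAP 14.1 on the severity standard. Either link the three-level scale to CTCAE explicitly or state that the three-level scale is the one used, and record any departure from the protocol in SAP section 16.

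The cost is one extra descriptive table, a one-line form revision and a few sentences of text. With 22 versus 11 subjects the table should be presented without tests.
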